6.3.6 Subgroup analyses

We will consider subgroups of incident vs. prevalent patients and subgroups of patients who were prescribed a diuretic (vs. not) prior to study start. Given the small sample, these analyses will be considered exploratory and models will be adjusted for baseline demographic and clinical factors.

6.3.7 Sensitivity analyses

We will conduct sensitivity analyses to test the robustness of our findings. Results of these analyses will be used to guide soundness of the main results. If the main results are demonstrated to be fragile, we will soften our conclusions around the main results as appropriate. Alternatively, if the main results are demonstrated to be robust, we will be confident in our main results conclusions. Specifically, we will conduct sensitivity analyses:

- excluding data from participants with endpoints drawn "off-schedule" (e.g. serum electrolytes, 24-hour urine, symptom assessment, etc.);
- excluding data with questionable values;
- testing for difference by clinic;
- evaluating the impact of variations on model assumptions and covariates;
- evaluating model residuals;
- testing for difference with transformations of scale and changes in the definitions of outcome variables

6.4 Sample Size and Power

We designed this pilot study to evaluate the safety, tolerability, and acceptability of furosemide use in HD patients and assess for furosemide efficacy and safety signals. We aim to enroll a sufficient number of participants to yield data supporting the efficacy, acceptability, tolerability, and safety of furosemide and to provide a basis for calculating the sample size of a future randomized trial. Sample size considerations were framed using standard study design parameters to ensure 80% power to detect pre-specified effect sizes utilizing intermediate outcomes.

With a sample size of 36 patients, we have 83% power to detect a mean change in urine volume from baseline of at least 5 ml/24-h, assuming a change S.D. = 10 ml/24-h¹⁷ and a 2-sided α = 0.05 (>99% power for urine volume change of 10 mL/24-h). With 30 patients, we have 99% power to detect a mean change in urine volume from baseline of at least 10 mL/24-h. Sample size calculation estimates were based on existing data about expected response to furosemide and S.D.s observed in other studies of urine volume in HD patients.¹⁷

Our goal sample size is 36 participants. We will account for dropout by enrolling up to 40 participants. If fewer than 30 participants are eligible for period 2 at the end of the period 1 dose titration period (i.e. participants who did not

tolerate or accept furosemide in period 1), we will recruit additional participants to maintain a sample size over 30 participants for the follow-up period.

6.5 Interim Analysis

No interim analysis is planned. See *Section 7* for safety management plans.

7 SAFETY MANAGEMENT

7.1. Definitions

Definitions are per the January 2007 Guidance on Reviewing and Reporting Unanticipated Problems Involving Risks to Participants or Others and Adverse Events, Office on Human Research Protection (OHRP) Guidance. http://www.hhs.gov/ohrp/policy/advevntguid.html

7.1.1. Adverse Event

An *adverse event (AE)* is any untoward or unfavorable medical occurrence in a human study participant, including any abnormal sign (for example, abnormal physical exam or laboratory finding), symptom, or disease, temporally associated with the participant's involvement in the research, whether or not considered related to the participant's participation in the research.

7.1.2. Serious Adverse Event

A serious adverse event (SAE) is any AE that is:

- fatal or results in death
- life-threatening
- requires inpatient hospitalization (>24 hours) or prolongs existing hospital stay
- results in persistent or significant disability or incapacity
- results in congenital anomalies or birth defects
- an important medical event*

*Important medical events are those that may not be immediately life threatening but are clearly of major clinical significance.

7.1.3. Unanticipated Problems Involving Risk to Participants or Others

(See also Section 7.3.4)

An Unanticipated Problem is any incident, experience, or outcome that meets all the following criteria:

• unexpected (in terms of nature, severity, or frequency) given the research procedures that are described in the IRB-approved research protocol and informed consent document and the characteristics of the participant population being studied;

• related or possibly related to participation in the research; possibly related means that there is a reasonable possibility that the incident, experience or outcome may have been caused by the procedures involved in the research, and

• suggests that the research places participants or others at a greater risk of harm (including physical, psychological, economic, or social harm) related to the research than was previously known or recognized.

7.2. Adverse Event Tracking Period

The study period during which AEs must be tracked and reported is normally defined as the period from the initiation of study procedures to the end of the study treatment follow-up. For this study, the study treatment follow-up is 2 weeks following the last dose of study drug.

7.2.1. Post-study Adverse Event

All unresolved adverse AEs will be followed by the investigator until the events are resolved, the participant is lost to follow-up, or the AE is otherwise explained. At the last scheduled visit, the investigator will instruct each participant to report any subsequent event(s) that the participant, or the participant's personal physician, believes might reasonably be related to participation in this study. The investigator will notify the study monitor of any death or AE occurring at any time after a participant has discontinued or terminated study participation that may reasonably be related to the study. The sponsor (NIDDK) will also be notified if the investigator should become aware of the development of cancer or of a congenital anomaly in a subsequently conceived offspring of a participant that has participated in this study.

7.3. Recording of Adverse Events

At each contact with the participant, the investigator or site designee will seek information on AEs by specific questioning and, as appropriate, by examination. Information on AEs will be recorded in the source document, and also on the AE log case report form (CRF). All signs, symptoms, and abnormal diagnostic procedure results relating to the same event will be recorded under one diagnosis name.

7.3.1. Adverse Events of Interest

The following AEs are anticipated in patients treated with furosemide and will be recorded on the appropriate AE of Interest CRF. See *Section 7.3.2* for definitions.

- Hypokalemia
- Hypocalcemia
- Hypomagnesemia
- Hypotension
- Hearing change
- Tinnitus
- Rash

If the event meets the definition of serious as defined in *Section 7.1.2*, it will be recorded on an SAE form in addition to the appropriate AE of special interest CRF. Participants will be assessed for the occurrence of AEs of Interest at study visits (weekly during dose escalation and every other week during follow-up). The clinical course of each event will be followed until resolution, stabilization, or until it has been determined that the study treatment or participation is not the cause.

7.3.2. Trial-Defined Adverse Events

The HD population undergoes frequent laboratory testing and has a high rate of peri-dialytic hypotensive events requiring changes in the dialysis prescription, adjustment of estimated dry (target) weight, or change in dialysis-related medications. Due to the unique nature of this population, the following events are considered routine aspects of maintenance HD therapy and will not be recorded as an AE except as noted:

- Anemia will be reported when hemoglobin is <7.5 mg/dL
- Hypokalemia will be reported when potassium level <3.2 mEq/L
- Hyperkalemia will be reported when potassium level ≥6.6 mEq/L
- Hypomagnesemia will be reported when magnesium level <0.8 mEq/L
- Hyperphosphatemia will be reported when phosphorous >9.5 mg/dL

- Hypocalcemia will be reported when serum corrected calcium <7.0 mg/dL
- Hypercalcemia will be reported when serum corrected calcium >11.0 mg/dL
- Hyperparathyroidism will be reported when PTH >1200 pg/mL
- Hypotension will be reported when it meets the criteria for serious dialysis-associated hypotension (hypotension requiring hospitalization or treatment in an emergency room and not attributable to overt sepsis, acute myocardial infarction, or other cardiovascular event (e.g. aortic dissection))
- Hearing change will be reported if Inner EAR score decreases by 10 points from baseline
- Tinnitus- will be reported at level of severe or very severe patient-reported tinnitus
- Rash- will be reported at level of severe or very severe patient-reported rash

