Occurrence of any of the following events will end dose up-titration: 1) electrolyte abnormalities (serum potassium <3.2 mEq/L, serum magnesium <0.8 mEq/L, and/or serum corrected calcium <7 mg/dL); 2) side effects attributable to furosemide (severe or very severe rash, tinnitus, or hearing change); decrease in Inner Effectiveness of Auditory Rehabilitation (Inner EAR) instrument score by more than 10 points; and/or intradialytic systolic BP <80 mmHg that a study investigator attributes to study drug-induced hypovolemia); and/or 3) patient non-acceptance (defined as the

patient reporting unwillingness to take the study drug). If one of these events occur, the participant will return to the prior tolerated oral furosemide dose. If one of these events occurs at the lowest administered dose, oral furosemide will be stopped and not re-started.

During the 12-week follow-up period (period 2), participants who tolerated and accepted furosemide in period 1 will continue their maximally tolerated period 1 furosemide dose during the 12-weeks of follow-up. If a participant has electrolyte abnormalities or other side effects attributable to furosemide in period 2 (i.e. on their period 1 maximally tolerated dose), the dose will be lowered sequentially (i.e. dose de-escalation: $160 \rightarrow 120 \rightarrow 80$ mg twice daily, or, if on alternative dosing due to prior diuretic use, decrease dose by 50%, rounded to the nearest whole tablet strength of existing (i.e. available) furosemide tablet formulations, until tolerated). If side effects persist or if the participant chooses, oral furosemide will be stopped.

Investigational New Drug (IND) exemption status

Oral furosemide is marketed as a prescription drug product and regulated by the U.S. FDA. Furosemide is indicated for edema and hypertension (signs and symptoms of volume overload). Its use in this study will be considered an on-label use. Our study is exempt from IND requirements for the following reasons:

- Oral furosemide is lawfully marketed in the U.S.
- The study is not intended to be reported to the FDA as a well-controlled study in support of a new indication for use and is not intended to be used to support any other significant change in the labeling for the drug.
- The study is not intended to support a significant change in the advertising for the product.

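### Section 7.3.2 has no AE-recording criterion for severe patient-reported hearing change, although that symptom ends up-titration and is a primary safety endpoint

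*Combined protocol and SAP*

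**What the plan says.** Section 7.1.1 defines an AE broadly, as "any untoward or unfavorable medical occurrence in a human study participant, including any abnormal sign", and it includes symptoms. Section 7.3.1 then names seven AEs of interest, hearing change, tinnitus, rash and hypotension among them: "The following AEs are anticipated in patients treated with furosemide and will be recorded on the appropriate AE of Interest CRF". It takes their definitions from 7.3.2.

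Section 7.3.2 lists events regarded as a normal part of maintenance hemodialysis, which "will not be recorded as an AE except as noted". The exceptions that matter here are:

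- Hearing: "Hearing change will be reported if Inner EAR score decreases by 10 points from baseline".
- Tinnitus: "Tinnitus- will be reported at level of severe or very severe patient-reported tinnitus". Rash has a matching line at the same severity.
- Hypotension: "Hypotension will be reported when it meets the criteria for serious dialysis-associated hypotension", meaning hospital or emergency room care.

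The titration rule in 1.2, repeated in 3.5.2 and 4.3, stops up-titration for "side effects attributable to furosemide (severe or very severe rash, tinnitus, or hearing change". A fall in the Inner EAR score is named there as a further trigger. The participant returns to the last tolerated dose, or stops furosemide if the event occurs at the lowest dose.

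**The concern.** Rash, tinnitus and hearing change are handled as one group of toxicity symptoms in the titration rule and in the primary safety endpoints. Only in 7.3.2 are they separated. Because 7.3.2 removes its listed events from AE recording unless a criterion is met, and gives hearing change an Inner EAR criterion alone, a severe hearing symptom without a 10-point fall has no route to the AE-of-interest form.

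The result is odd. A symptom that 7.3.2 does not list, such as nausea, stays an AE under the general definition, while a severe hearing symptom drops out because it is listed. Section 1.3.1 says that furosemide ototoxicity can end in permanent deafness. The general reason given in 7.3.2, frequent laboratory testing and peri-dialytic hypotension, has nothing to do with hearing.

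What is at stake is the AE record. Section 7.3.1 attaches follow-up to resolution or stabilization to AEs of interest. Section 7.6.2 sends accumulated AEs of interest and overall AE rates to the monthly team meeting. It also describes the external monitor's detailed review, including relationship to drug and action taken, for AEs and SAEs.

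**Working it through.** The plan states no figure on this point, so the check sets the provisions side by side.

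| Provision | Rash | Tinnitus | Patient-reported hearing change | Inner EAR fall |
|---|---|---|---|---|
| Ends up-titration (1.2, 3.5.2, 4.3) | severe or very severe | severe or very severe | severe or very severe | more than 10 points |
| Primary safety endpoint (6.1) | severe or very severe | severe or very severe | severe or very severe | 10 points |
| AE to monitor (7.6.2) | yes | yes | yes | presumably, as objective hearing change |
| AE-recording criterion (7.3.2) | severe or very severe | severe or very severe | **none** | 10 points |

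Only the patient-reported hearing column has an empty cell.

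**Other routes into the AE record.** Section 7.3.3 makes a change of dose a ground for recording, but only for laboratory abnormalities. Section 7.1.2 would admit the event as an SAE if it were judged an important medical event, which is discretionary. Neither is a criterion for the symptom.

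**Schedule (4.4).** Self-reported symptoms are asked at weeks 1, 2, 3, 4, 5, 6, 8, 10, 12, 14, 16 and 18, which is 12 visits. The Inner EAR is given at weeks 2, 4, 6, 10, 14 and 18, which is 6 visits. The difference, 12 − 6 = 6 visits (weeks 1, 3, 5, 8, 12 and 16), has self-report only. Section 7.3.1 says AEs of interest are assessed weekly in dose escalation and every other week in follow-up, which is the symptom schedule. At half of those visits the sole hearing criterion cannot be applied from scheduled data.

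Timing is nonetheless secondary. In period 1 each dose decision (weeks 2, 4 and 6) has an Inner EAR. In period 2 the 3 self-report-only visits (weeks 8, 12 and 16) are each followed by an Inner EAR two weeks later (weeks 10, 14 and 18), so a sustained 10-point fall would still be recorded. The gap is the missing self-report criterion.

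**Hypotension, for comparison.** Intradialytic systolic BP below 80 mmHg that an investigator attributes to drug-induced hypovolemia ends up-titration, with no hospital or emergency room condition. Section 7.3.2 records hypotension only when that condition is met. A drug-attributed event managed in the clinic during period 1 therefore changes the dose plan without an AE criterion. The endpoint in 6.2 counts systolic BP below 80 mmHg, but without attribution or dose action.

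**The case against.** The best defense of the hearing line is in 7.1.5 (ototoxicity management, under 7.7), which declares an Inner EAR fall of at least 10 points to be clinically significant hearing loss. On that view 7.3.2 applies a defined threshold on purpose. The Inner EAR is itself patient-rated, with 11 items and stated reliability. The symptom form has a single item on hearing change with no direction, framed around dialysis treatments. Tinnitus and rash have no such scale, which could explain their different wording. There are also backstops: any self-reported hearing loss goes to audiometry (1.3.1, 7.1.5), 7.5 has investigators watch all safety endpoints and update the monitor, and an audiometry-confirmed loss could arguably be logged under 7.3.

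This explains why an Inner EAR threshold is there. It does not explain why the symptom is left out, since the same single item is trusted to end up-titration and to count as a primary endpoint. Section 7.6.2 also names the symptom as a separate AE to monitor. The backstops limit the loss but create no recording criterion.

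A reader might infer three stronger claims that the documents do not support.

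- **Hearing safety data are lost.** They are not: the symptom form collects them and 6.1 analyzes them.
- **The hypotension exclusion is an error of the same kind.** It is a stated choice. Section 7.3.2 explains that peri-dialytic hypotension is frequent, "requiring changes in the dialysis prescription, adjustment of estimated dry (target) weight, or change in dialysis-related medications". That reason does not mention study-drug dose changes, so a narrow gap remains in period 1. It does not clearly extend to period 2: 4.3 glosses tolerance there in terms of serious hypotension, and 7.1.4 places study-drug dose reduction within the management of serious hypotension, which 7.3.2 already records.
- **A count of titration triggers with no AE counterpart measures the size.** It would count wordings, not events.

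**Conclusion.** The hearing point holds. Section 7.3.2 conflicts with 6.1, 7.6.2 and the titration rule, and 7.1.5 does not resolve the conflict. The consequence is limited to AE-of-interest forms, AE rates, follow-up to resolution and the external monitor's detailed AE review. Endpoint capture, dosing decisions and audiometry referral stand as planned.

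This rests on two assumptions: that staff follow 7.3.2 literally, and that some participants report a severe or very severe hearing change without a 10-point Inner EAR fall at a scheduled assessment. The documents give no rate for that combination, so the number affected cannot be estimated and could be zero. The correction is still worth making, because the pilot's stated focus in 7.5 is safety and tolerability, and the AE listings should show why a participant was stepped down or stopped.

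The hypotension item is an optional improvement for period 1 only.

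**What to change.** In 7.3.2, extend the hearing line so that hearing change is reportable in either of two cases: the Inner EAR score falls by at least 10 points from baseline, or the patient rates a hearing change as severe or very severe (3 or 4 on the symptom form in 13.1). Writing the threshold as at least 10 points also matches 2.1 and 7.1.5. For consistency, 1.2, 3.5.2 and 4.3, which now say more than 10 points, could use the same wording.

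Optionally, for period 1, complete an AE-of-interest form with attribution and dose action when intradialytic systolic BP below 80 mmHg attributed to the study drug ends up-titration. Leave routine hypotension off the log as planned.

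The cost is a wording edit and a few more forms. Symptoms and BP are already collected, and attribution of low BP is already made for the titration decision. The downside is a slightly higher AE count.

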7.3.3. Abnormal Laboratory Values

A clinical laboratory abnormality should be documented as an AE if:

- The laboratory abnormality is not otherwise refuted by a repeat test that was performed specifically to confirm the abnormality
- The abnormality suggests a disease and/or organ toxicity
- The abnormality is of a degree that requires active management; e.g. change of dose, discontinuation of the drug, more frequent follow-up assessments, further diagnostic investigation, etc.
- The abnormality meets the criteria in *Section 7.3.2.*

7.3.4. Anticipated Adverse Events

The following AEs are anticipated in the HD population and will not be considered to be Unanticipated Problems. Note that the designation as "Anticipated" does not imply that the event is not an SAE but relates to the regulatory definition of Unanticipated Problems as provided in *Section 7.1.3*.

- Death
- Coronary Ischemia including:
 - o Unstable angina
 - o Acute MI
 - o Coronary revascularization
- Heart failure hospitalization or exacerbation
- Cardiac arrest
- Cardiac arrhythmia (ventricular or atrial)
- Peripheral vascular revascularization
- Amputation
- Vascular Access Events Including:
 - o Catheter exchange, removal or declotting
 - o Arteriovenous graft or fistula complications
 - o Clotting
 - o Stenosis
 - o Revascularization
 - o Infection
- Infections Including:
 - o Pneumonia
 - o Vascular access infection
 - o Bacteremia
 - o Clostridium difficile infection

7.4. Reporting of Serious Adverse Events and Unanticipated Problems

The investigator will report SAEs and Unanticipated Problems to the safety monitor within 24 hours of first knowledge of the event. To report such events, an SAE form or an Unanticipated Problem form will be completed by the investigator and sent to the safety monitor. The safety monitor will facilitate the timely medical review and reporting of the event in accordance with study policies and IRB requirements. The investigator will keep a copy of the SAE form / Unanticipated Problem form on file at the study site. At the time of the initial report, the following information should be provided:

- Study identifier
- Participant identifier
- A description of the event
- Date of onset
- Current status
- Whether study treatment was discontinued
- The reason why the event is classified as serious
- Investigator assessment of the association between the event and study treatment

Within the following 7 days, the investigator will provide further information on the SAE or the unanticipated problem in the form of a written narrative. This should include a copy of the completed SAE form or Unanticipated Problem Form, and any other diagnostic information that will assist the understanding of the event. Significant new information on ongoing serious AEs should be provided promptly to the safety monitor.

SAEs that are still ongoing at the end of the study period must be followed up to determine the final outcome. Any SAE that occurs after the study period and is considered to be possibly related to the study treatment or study participation should be recorded and reported immediately.

7.4.1. Investigator Reporting to the IRB

Investigators will report SAEs and Unanticipated problems to the IRB in accordance with the Office of Human Research Protections (OHRP) guidelines. OHRP recommends that:

1) Unanticipated problems that are SAEs should be reported to the IRB within 1 week of the investigator becoming aware of the event; and

2) Any other unanticipated problem should be reported to the IRB within 2 weeks of the investigator becoming aware of the problem.

Reporting Process

Unanticipated problems posing risks to participants or others as noted above will be reported using the appropriate IRBdesignated form or as a written report of the event (including a description of the event with information regarding its fulfillment of the above criteria, follow-up/resolution and need for revision to consent form and/or other study documentation). Copies of each report and documentation of IRB notification and receipt will be maintained in the study files.

Other Reportable events:

- Any adverse experience that, even without detailed analysis, represents a serious unexpected AE that is rare in the absence of drug exposure (such as agranulocytosis, hepatic necrosis, Stevens-Johnson syndrome).
- Any AE that would cause the sponsor to modify the investigators brochure, protocol or informed consent form, or would prompt other action by the IRB to assure protection of human participants.
- Information that indicates a change to the risks or potential benefits of the research, in terms of severity or frequency.

• Change in FDA safety labeling or withdrawal from marketing of a drug, device, or biologic used in a research protocol.

• Breach of confidentiality

• Change to the protocol taken without prior IRB review to eliminate apparent immediate hazard to a research participant.

• Incarceration of a participant when the research was not previously approved under Subpart C and the investigator believes it is in the best interest of the participant to remain on the study.

• Complaint of a participant when the complaint indicates unexpected risks or the complaint cannot be resolved by the research team.

• Protocol violation (meaning an accidental or unintentional deviation from the IRB approved protocol) that in the opinion of the investigator placed one or more participants at increased risk, or affects the rights or welfare of participants.

